9.3.5 Disease-Related Events and/or Disease-Related Outcomes Not Qualifying as AEs or SAEs

There are no protocol-specific exceptions to the AE experience reporting presented in Section 9.3.

9.3.6 Pregnancy and Exposure During Breastfeeding

Although pregnancy and infant exposure during breastfeeding are not considered AEs, any pregnancy or infant exposure during breastfeeding in a participant (spontaneously reported to the investigator or their designee) that occurs during the study are reportable to the Sponsor.

All reported pregnancies must be followed to the completion/termination of the pregnancy. Pregnancy outcomes of spontaneous abortion, missed abortion, benign hydatidiform mole, blighted ovum, fetal death, intrauterine death, miscarriage and stillbirth must be reported as serious events (Important Medical Events). If the pregnancy continues to term, the outcome (health of infant) must also be reported.

9.3.7 Events of Clinical Interest (ECI)

Selected non-serious and serious adverse events are also known as Events of Clinical Interest (ECI) and must be reported to the Sponsor.

Events of clinical interest for this trial include:

1. an overdose of Sponsor's product, as defined in Section 9.4 – Treatment of Overdose, that is not associated with clinical symptoms or abnormal laboratory results.
2. first instance of ALT or AST >500 IU/L after initiation of study therapy through 14 days following treatment.*
3. first instance of ALT or AST >3x nadir AND >100 IU/L after initiation of study therapy through 14 days following treatment.*

*Note: The purpose of the criteria is to specify a threshold of abnormal hepatic tests that may require and additional evaluation for an underlying etiology. The trial site guidance for assessment and the follow up of these criteria can be found in the Investigator Trial File Binders (or equivalent).

Reporting requirements for ECIs are presented in [Table 8](#). Any ECI involving overdose or ALT/AST criteria are to be reported to the Sponsor within 24 hours.

9.4 Treatment of Overdose

In this trial, an overdose is any dose higher than the prescribed dose of EBR/GZR.

- FDC: 1 tablet once daily
- Pediatric Formulation: Dosage communicated (TBD as informed by PK Modeling)

No specific treatment is recommended for an overdose. Decisions regarding dose interruptions or modifications will be made by the investigator in consultation with the Sponsor Clinical Director based on the clinical evaluation of the participant.

9.5 Safety

Details regarding specific safety procedures/assessments to be performed in this trial are provided below.

Clinically significant findings from any safety assessments conducted prior to starting study therapy (eg, physical examinations, vital signs, and ECGs at screening) should be captured in the Medical History electronic case report form (eCRF). For safety assessments performed during study treatment or follow-up, any clinically significant changes compared with the assessments prior to study treatment must be captured as AEs. Participants may be asked to return for unscheduled visits in order to perform additional safety monitoring.

Planned time points for all safety assessments are provided in the SoA.

9.5.1 Physical Examinations

All physical examinations must be conducted as per institutional standard by the principal investigator or subinvestigator (physician, physician assistant, or nurse practitioner) as follows:

- A complete physical examination at screening and Day 1 to include the following assessments: general appearance, head, eyes, ears/nose/throat, neck, lymph nodes, skin, lungs, heart, abdomen, musculoskeletal, and neurologic evaluations. Breast, rectal, and genitourinary/pelvic examinations should be performed when clinically indicated.
- A focused physical examination at any other visit when clinically indicated.

Investigators should pay special attention to clinical signs related to previous serious illnesses.

Height and weight will be measured and recorded per the SoA and used by the Sponsor to calculate body mass index.

9.5.1.1 Height of Biological Parent(s)

The height of the biological parents will be collected between screening and Day 1. If biological parents are unable to be reached during that period the participant may continue in the trial. Later attempts during the trial will be made to collect these data. Biological parental consent must be signed prior to obtaining, using, and disclosing their personal data.

Every effort should be made to measure the height of both biological parents at the study site. If this is not feasible for some parents, a self-reported height will be acceptable. The participant may participate in the study without these data and/or consent to obtain, use, and disclose parental personal data.

9.5.2 Vital Signs

- Vital signs will be measured in a semi-recumbent position after 10 minutes rest and will include oral temperature, systolic and diastolic blood pressure, and heart rate.
- NOTE: Oral temperatures should be taken, but if oral is not possible, tympanic, rectal, or axillary temperatures may be taken.

9.5.3 Electrocardiograms

- Special care must be taken for proper lead placement and participants should be shaved as necessary. Participants should be resting in a semi-recumbent position for at least 10 minutes prior to having ECG readings obtained.

9.5.4 Date of Menarche

The date of menarche must be recorded for females who have previously experienced menarche. Once a date of menarche has been confirmed, the participant is considered to be a WOCBP. For prepubescent females, site staff should continue to review and record, as appropriate, at each visit during the treatment period.

9.5.5 Contraception Confirmation

Throughout the screening and treatment periods, precaution must be taken to avoid pregnancy in WOCBP. Confirmation must be obtained and documented by site personnel that WOCBP are using acceptable methods of contraception (see Appendix 5). This assessment must be documented in the participant's study chart at each specified visit.

9.5.6 Clinical Safety Laboratory Assessments

Refer to Appendix 2 for the list of clinical laboratory tests to be performed and to the SoA for the timing and frequency.

- The investigator must review the laboratory report, document this review, and record any clinically relevant changes occurring during the study in the AE section of the CRF. The laboratory reports must be filed with the source documents. Clinically significant abnormal laboratory findings are those which are not associated with the underlying disease, unless judged by the investigator to be more severe than expected for the participant's condition.
- All protocol-required laboratory assessments, as defined in Appendix 2, must be conducted in accordance with the laboratory manual and the SoA.
- If laboratory values from non-protocol specified laboratory assessments performed at the institution's local laboratory require a change in study participant management or are considered clinically significant by the investigator (eg, SAE or AE or dose modification), then the results must be recorded in the appropriate CRF (eg, SLAB).
- For any laboratory tests with values considered clinically significantly abnormal during participation in the study or within 14 days after the last dose of study treatment, every attempt should be made to perform repeat assessments until the values return to normal or baseline or if a new baseline is established as determined by the investigator.

9.5.6.1 Fibroscan®

This method for assessing liver cirrhosis has gained increasing acceptance. In the US, this methodology is FDA-approved and in other countries, it is often the preferred method of assessment. FibroScan® results are influenced by a number of confounders including ALT, ascites, and underlying disease. Hepatitis C is one of the best studied and is the disease state with the most reproducible/reliable results. FibroScan® has been evaluated in many liver diseases for the staging of liver fibrosis, and has been demonstrated to be very effective for differentiating cirrhosis (F4) from no cirrhosis (<F4), but it is less capable of differentiating gradations of fibrosis. In a large study by Castera et al. [Castera, L., et al 2008], in a population of participants with chronic HCV infection, a cut-off of 12.5 kPa was selected for

cirrhotics. At this cut-off, the sensitivity and specificity of the test for cirrhosis were 87% and 91%, respectively, and the negative predictive value was 95%. Since this analysis was assessed specifically in participants with chronic HCV infection, the cut-off value >12.5 kPa used by Castera was selected to include cirrhotics in the current study.

9.5.6.2 Pregnancy Testing

For WOCBP (see Appendix 5), a urine pregnancy test must be performed at the site on Day 1, with negative results prior to initiating study treatment. If the urine pregnancy test result is positive, a serum pregnancy test will be performed. If the result of the serum pregnancy test is positive, the participant must be excluded from the study per Section 6.1 – Inclusion Criteria.

Ongoing pregnancy testing will be conducted per the SoA. If the participant has a confirmed positive serum pregnancy test, study treatment must be discontinued per Section 8.1 – Discontinuation/Withdrawal Criteria and the pregnancy reported per Section 9.3.6 – Pregnancy and Exposure During Breastfeeding.

9.5.6.3 HIV Evaluation

HIV serology samples will be collected and processed for all participants at screening.

9.5.6.4 Hepatitis B Virus Evaluation

Samples will be collected from each participant to assess HBsAg and anti-HBc, at screening.

9.6 Pharmacokinetics

The decision as to which plasma samples collected will be assayed for evaluation of PK will be collaboratively determined by the department of Quantitative Pharmacology and Pharmacometrics and the appropriate department within Clinical Research. If indicated, these samples may also be assayed and/or pooled for assay in an exploratory manner for metabolites and/or additional PD markers.

PK samples will be collected in all pediatric participants. The proposed PK sampling scheme across all age groups is provided below in [Table 9](#).

9.6.1 Blood Collection for Plasma EBR/GZR

Sample collection, storage, and shipment instructions for plasma samples will be provided in the operations/laboratory manual.

Pharmacokinetic samples will be collected according to the PK sampling schemes shown in [Table 9](#). To avoid multiple venipunctures in pediatric participants, sites are encouraged to use a peripheral venous access port to collect multiple blood samples for intensive PK sampling. More details on this procedure for blood collection are provided in the Laboratory Manual.

On all PK visits where a predose sample will be collected, the visit should occur prior to the participant's regular time for taking their study medication and the participant should withhold their dose until after the visit. For predose PK visits (ie, Day 1, Week 4, Week 8), if it is not feasible to schedule the visit prior to the participant's regular time for taking their

study medication, the participant should withhold their dose until reporting to the clinic. The predose PK sample will be obtained and the dose will be administered at the clinic. The date and time of each PK sample as well as the date and time of the last dose of EBR/GZR prior to the PK sample will be recorded.

All PK samples will be used to evaluate PK exposures, and potentially also the PK-efficacy and PK-AE relationships of EBR and GZR. The date and time of each PK sample as well as the date and time of the last dose of EBR/GZR prior to the PK sample will be recorded.

The PK sampling schemes selected for Day 1 and TW4 facilitates the ability to estimate all PK parameters specified in the objectives. Day 1 intensive PK will be collected in Mini Age Cohort 1 to obtain an early estimate of AUC to confirm that the appropriate dose is selected for Mini Age Cohort 2. The PK sampling at TW8 facilitates an assessment of PK exposure when ALT and/or AST elevations are anticipated to be maximal, if there are elevations.

The total blood volume required for PK analyses of both GZR and EBR (combined) is 1 mL per sample. The recommendations on safe blood sample volume limits for pediatric clinical research is provided in literature [Jack, R. 2001]. The total blood volume at each visit, accounting for PK and other sample collections is below the maximum blood limit requirements per blood draw on each visit. Also, the total blood volume collected within any 30-day period is below the maximum blood limit requirements.

Recording and Entering Meal/Soft Food Vehicle Information

- Participants will be provided an SMD which contains instructions for recording meal data that includes what they eat/drink and the time of the meal. Participants or an observer (legally acceptable representative/caregiver) should record ALL meal data from 48 hours BEFORE the PK visit through the day of the PK visit.
- Participants receiving EBR/GZR pediatric formulation should record the soft food that EBR and GZR granules were mixed into as well as the pediatric formulation food consumption timeframe (ie, the time from mixing of medication into the soft food vehicle to complete consumption of all granules that were mixed into the soft food). Participants or an observer should record this information in the SMD for all doses.
- The site will be responsible for entering the appropriate data from the SMD, as well as the qualitative fat content of the meal, in the eCRF according to the eCRF Entry Guidelines. Meal data should be entered by the site as follows:
 - For visits on Day 1 (there will be no meal data entry for pre-dose sample on Day 1), Week 4, and Week 8:
 - Enter all meal data within **2 hours before, and up to 1 hour after** the EBR/GZR dose administered on the day **prior** to the predose PK visit.
 - Enter all meal data within **2 hours before, and up to 1 hour after** the EBR/GZR dose administered at the study site.

- For participants who may take multiple meals during the time window, a separate meal entry is recorded on the eCRF for each meal within the window.
 - The soft food vehicle as well as the pediatric formulation food consumption timeframe recorded in the SMD for each dose of pediatric formulation should be entered in the eCRF.

Table 9 Pharmacokinetic Sampling Timepoints for All Age Cohorts

Study Day/Week	Time Relative to Last Dose of EBR/GZR^{1,2}
Day 1	Mini Age Cohort 1: Predose and 0.5, 1, 2, 3, 4, 6, 8, 10, 24 hr postdose All other Cohorts: Predose, 2 hr, 4 hr postdose
Week 4	All Cohorts: Predose and 0.5, 1, 2, 3, 4, 6, 8, 10, 24 hr postdose
Week 8	All Cohorts: Predose and 2 hr postdose
HCV Viral Failure Confirmation Visit (if applicable)	All Cohorts: Anytime
Early Discontinuation Visit (if applicable)	All Cohorts: Anytime
1 mL of blood will be collected at each specified time point for plasma PK assessments of EBR/GZR (1 mL whole blood is enough for both analytes)	

¹ The date and time of the last EBR/GZR dose prior to each PK sample collected must be recorded in INFORM

² The time of each PK sample collection relative to last dose of EBR/GZR must be recorded in INFORM

Note: At the time of PK sample collection, reference the participant's Study Medication and Meal Diary to obtain the date and time of the last dose of EBR/GZR, prior to the PK sample collection. The participant (or their caregiver, surrogate, or legally acceptable representative) should be asked to confirm the date and time are correct.

9.7 Pharmacodynamics

Pharmacodynamic parameters will not be evaluated in this study.

9.8 Future Biomedical Research Sample Collection

The following specimens are to be obtained as part of Future Biomedical Research:

Leftover main study plasma from HCV RNA stored for future research.

Leftover main study plasma from viral resistance stored for future research.

9.9 Biomarkers

Biomarkers will be evaluated as part of the Future Biomedical Research sub-study.

9.10 Palatability and Acceptance Assessment

The PAA (see Appendix 7) is to be completed for all participants at the time of EBR/GZR administration at TW4 and TW8 of the study. The PAA should be implemented with the following recommendations:

- **Ages 3-4 years:** Completion by an observer (legally acceptable representative/caregiver/healthcare provider).
- **Ages 5-13 years:** Combined completion where the participant completes the faces question, and the observer completes the remaining questions.
- **Ages 14-18 years:** Completion directly by the participant, preferred when possible.

Observer assessments should be based on what the legally acceptable representative/caregiver/healthcare provider has observed directly during and after medication administration, including the participant's facial expressions, behavior, and what the participant says. Only individuals who have actually observed the participant taking the medication should complete the assessment.

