Visit Number>Title	1	2	3	4	5	6	7	8	9	10	11	12	13	14	15	16	Day 1 procedures to be performed prior to 1 st morning dose unless otherwise specified. FW8, FW16, & FW20 are via phone contact w/the participant or the participant's legally acceptable representative to make sure he/she is doing well and FW24 visit reminder	
Scheduled Hour, Day, Week, etc., and Window:	-45	NA	TW4: -3 to +3 days All other TW: -7 to +7 days							-2 to +2 weeks							NA	Participants should be allocated within a 45 day screening window
Chemistry (complete)	X	X		X	X		X			X			X	X	X			
Chemistry (abbreviated)			X		X		X		X								Abbreviated blood chemistry includes only ALT, AST, Alkaline phosphatase, T. Bili, Albumin, GGT, CPK	
Hematology	X	X		X		X		X	X		X			X	X	X		
HIV Serology	X																	
Urinalysis		X		X		X		X	X							X		
Hepatitis B Virus Evaluations																		
HBSAg	X																	
Anti-HBc	X																	
Patient-reported Outcome																		
Palatability and Acceptance Assessment				X		X												

Trial Period	Screening	Treatment							Follow-up							Unscheduled		Notes
		Day 1	TW 2	TW 4	TW 6	TW 8	TW 10	TW 12	FW 4	FW 8	FW 12	FW 16	FW 20	FW 24	Unshed/ HCV VF Conf Visit	Early Discon Visit		
Visit Number/Title	1	2	3	4	5	6	7	8	9	10	11	12	13	14	15	16	Day 1 procedures to be performed prior to 1 st morning dose unless otherwise specified. FW8, FW16, & FW20 are via phone contact w/the participant or the participant's legally acceptable representative to make sure he/she is doing well and FW24 visit reminder	
Scheduled Hour, Day, Week, etc., and Window:	-45	NA	TW4: -3 to +3 days All other TW: -7 to +7 days							-2 to +2 weeks							NA	Participants should be allocated within a 45 day screening window
Pharmacokinetics (PK)																		

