5.4.2.2 Palatability and Acceptance Assessment Endpoint

Adherence to treatment for chronic HCV infection is necessary for participants to achieve SVR. Palatability may play an important role in adherence to HCV treatment in the pediatric population. Palatability is an important element in the determination of acceptability, and encompasses a product's smell, taste, aftertaste, and texture. Acceptability, including palatability, of EBR/GZR will be assessed in all participants using the Palatability Acceptance Assessment (PAA). In previous studies, the most commonly reported assessment measured palatability preference using a visual analog scale that was modified by including a facial hedonic scale (FHS; facial expression scale depicting various degrees of pleasure) [Thompson, C., et al 2015]. The five-point FHS for taste is one of the most frequently reported types of palatability assessments used in pediatric clinical trials.

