9.1.8 Treatment Administration

Participants in Mini Age Cohort 1 must be able to demonstrate the ability to swallow the adult FDC placebo tablet in order to be eligible for the trial. Prior to allocation, administration of the placebo to EBR/GZR FDC tablet will be witnessed by the investigator and/or study staff to participants who have met all other eligibility criteria for allocation into Mini Age Cohort 1. If it is determined by PK analysis that Expanded Age Cohort 1 will also receive the adult FDC dose, administration of the placebo FDC tablet will be witnessed by the investigator and/or study staff to participants in Expanded Age Cohort 1. Participants in this Age Cohort that cannot swallow the placebo FDC tablet are not eligible to be allocated into the trial.

Following completion of the Day 1 procedures per SoA (Section 2) and confirmation of eligibility, the site pharmacist or study coordinator will contact the IVRS/IWRS for treatment allocation.

NOTE: Sites should not call IVRS/IWRS for treatment assignment until the participant has met all criteria for the study and are ready to receive the first dose of study medication on Day 1.

Administration of the following doses will be witnessed by the investigator and/or study staff during the site visit:

- First dose of study medication at Day 1 for all participants.
- TW4
- TW8

All other dosing will be performed by the participant/legally responsible representative (ie, unsupervised at his/her home) and recorded on the participant's SMD.

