10.6.5.4 Palatability and Acceptance Assessment

Each participant will rate the palatability and respond to questions on the acceptability of treatment with EBR/GZR on TW4 and TW8 of the study. This will be based on the FHS facial expression scale depicting various degrees of pleasure as an assessment of palatability (Section 5.4.2.2 and Section 9.10).

Descriptive statistics will be used to summarize the palatability and acceptability responses. Missing data will not be imputed, and the analyses will be based on observed data only. These analyses will be based on the FAS population.

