12.7 Appendix 7: Palatability and Acceptance Assessment Form

THE COMBINATION REGIMEN OF GRAZOPREVIR (GZR)/ELBASVIR (EBR) +/- RIBAVIRIN
(RBV) IN PEDIATRIC SUBJECTS WITH CHRONIC HEPATITIS C INFECTION

PAA

Compound MK-5172	Protocol 079	Visit	Screening No. (Site - Sequence No.) _____	Randomization No. _____
----------------------------	------------------------	-------	----------------------------------------------	----------------------------

PALATABILITY AND ACCEPTANCE ASSESSMENT (PAA)				
Specify completion date: _____ DD-Mon-YYYY				
Please mark one box below to identify the person entering the responses on the questionnaire.  The patient  The patient/primary caregiver  The patient and parent/primary caregiver  The health care provider (e.g., physician, nurse, medical assistant or nursing assistant caring for the patient)				
This form should be completed at the time of oral medication administration. Please answer all questions.				
1. Please mark the box of one picture below to show how you/the patient feels about the taste of the medication:   Very bad  Bad  Neither good nor bad  Good  Very Good				
2. Please indicate if you/the patient had any of the following problems when taking the medication by mouth: a. Refusing  Yes  No b. Spitting Out  Yes  No c. Throwing Up or Spitting Up  Yes  No d. Gagging  Yes  No e. Other, specify _____				
3. Are there any other comments related to the taste of the medication?  Yes  No Specify comments: _____ _____ _____				
I confirm this information is accurate.	Subject's/Caregiver's Initials: _____			Date: _____

I have reviewed this information.	Staff Initials: _____	Date: _____
------------------------------------------	-----------------------	-------------

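### Palatability is rated only at TW4 and TW8 and summarised on observed data, so children who stop before TW4 supply no rating; any who stop for taste or refusal would bias this exploratory result toward acceptability

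*Combined protocol and SAP*

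**What the plan says.** Evaluating palatability and acceptability is an exploratory objective in Section 4, with a palatability-scale score as its endpoint. Section 5.4.2.2 gives the reason for collecting it: "Palatability may play an important role in adherence to HCV treatment in the pediatric population". The same section says that acceptability "will be assessed in all participants using the Palatability Acceptance Assessment (PAA)".

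Section 9.10 fixes the timing: the form "is to be completed for all participants at the time of EBR/GZR administration at TW4 and TW8 of the study". The Schedule of Activities agrees. Its PAA row is marked at TW4 and TW8, with nothing at Day 1, TW2 or the Early Discontinuation visit. The form in Appendix 7 adds: "This form should be completed at the time of oral medication administration". It asks for a five-point taste rating and for yes/no answers on refusing, spitting out, throwing up and gagging.

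On analysis, Section 10.6.5.4 states: "Missing data will not be imputed, and the analyses will be based on observed data only". It then adds: "These analyses will be based on the FAS population". Section 10.5.2 defines the FAS as all allocated participants with at least one dose.

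Two other provisions matter. Section 9.1.8 lists the doses that staff witness, beginning with: "First dose of study medication at Day 1 for all participants". Section 6.5 lets the sponsor replace a participant who stops treatment before the TW4 intensive PK sampling.

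**The concern.** The children most likely to find the granules unacceptable are also the most likely to have stopped before anyone asks them. A child off treatment at TW4 takes no dose there, and the form is tied to a dose, so no rating is possible. The observed-only rule then drops that child without trace from the palatability summary, and the FAS label does not bring the child back. This is missingness that may depend on the outcome itself.

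Early rejection is plausible. The planned starting dose in Mini Age Cohort 2 is 30 mg/60 mg (Section 5.5.1), and packets hold 5 mg EBR or 10 mg GZR with 10 granules each (Section 7.1). That is 30/5 + 60/10 = 12 packets, or 120 granules, in soft food each day. Tablet users must swallow a placebo tablet before allocation. Granule users have no such check and may not change formulation.

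At stake is the trial's description of how acceptable the paediatric formulation is. The PK, safety and SVR₁₂ results do not depend on it.

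**Working it through.** **No figure to reproduce.** The plan gives no sample size, precision or expected rate for palatability, and no rate of early stopping for taste or refusal.

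**Inputs**
- N, granule users: Section 10.1 gives about 34 in the two younger cohorts, with 12 to 22 in each. Table 2 agrees: 7 + 7 + 20 = 34.
- k, children who stop before TW4 for taste or refusal: not in the documents; assumed 0 to 5.
- x, children rated at TW4 as finding the product acceptable: assumed about 90% of those rated.
- The acceptable/not acceptable split is a device for this illustration. The plan defines only a scale score and descriptive statistics.

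**Formulas**
- Observed-only result, as planned: x/(N − k).
- Result with early stoppers counted as not acceptable: x/N.
- Difference: x/(N − k) − x/N = [x/(N − k)] × (k/N). With about 90% acceptable and N = 34, each stopper adds about 0.90/34 = 2.6 points.

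**Results**

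| N | k | Observed only | Stoppers counted | Difference (points) |
|---|---|---|---|---|
| 34 | 0 | 31/34 = 91.2% | 31/34 = 91.2% | 0 |
| 34 | 1 | 30/33 = 90.9% | 30/34 = 88.2% | 2.7 |
| 34 | 3 | 28/31 = 90.3% | 28/34 = 82.4% | 8.0 |
| 34 | 5 | 26/29 = 89.7% | 26/34 = 76.5% | 13.2 |
| 12 | 1 | 10/11 = 90.9% | 10/12 = 83.3% | 7.6 |
| 12 | 2 | 9/10 = 90.0% | 9/12 = 75.0% | 15.0 |

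The rows for 12 use the smallest younger-cohort size and apply if results are shown by cohort.

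**Replacement.** If one stopper is replaced by a child who is rated, 34 ratings exist but 35 children were treated: 31/34 = 91.2% against 31/35 = 88.6%, a difference of 2.6 points. The bias is nearly unchanged, but the number of ratings no longer looks short.

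**How likely is at least one such stop among 34?** With true rate p the probability is 1 − (1 − p)^34: 29% at p = 1%, 50% at 2% and 83% at 5%. These rates are assumptions.

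**The case against.** Much of the case on the other side stands.

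- **Children who struggle but continue are rated.** A reader might infer that every child who rejects the granules in the first month goes uncounted. The documents do not support that. Only children no longer dosing at TW4 are missed. One who refuses, spits out or gags but carries on is asked about exactly those problems at TW4.
- **Early stoppers are visible elsewhere.** The reason for discontinuation is collected (Section 9.11.4) and primary reasons are displayed (Section 10.6.5.1). Dosing diaries are checked at each treatment visit, and AEs are reported from allocation. What remains is that none of these carries a taste score or is linked to the palatability summary. Percent compliance does not fill the gap either: for a child who leaves the study permanently, its denominator ends at the last dose (Section 10.11).
- **The bias is conditional.** A reader might also infer that acceptability is bound to be overstated. With no stops for taste or refusal before TW4, the bias is zero, and the documents do not say how many to expect.
- **It is small beside the imprecision.** For 28/31 the exact (Clopper-Pearson) 95% interval is about 74% to 98%, which contains the 82.4% obtained by counting three stoppers. That supports low priority, but the interval does not allow for a bias that always runs in one direction.
- **The timing may be deliberate.** Acceptability under repeated dosing differs from reaction to a first dose, and the sections agree with one another on TW4 and TW8. A Day 1 rating would supplement those visits, not replace them. Section 10.6 defers methods for exploratory objectives to a supplemental SAP, which may say more, but Section 10.6.5.4 already fixes the observed-only rule.
- **The present form does not suit Early Discontinuation.** It must be completed when a dose is taken, and medication is retrieved at that visit. This objection stands in full.

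**Conclusion.** The point holds as a low-priority improvement. Children who stop before TW4 are in the FAS without palatability data, so the assessment in all participants described in Section 5.4.2.2 is not achieved for them. If any of them stop for taste or refusal, the summary is biased toward acceptability: about 3 points per stopper among some 34 granule users, 7 to 8 points for one stopper in a cohort of 12, and nothing if there are none. These sizes rest on assumed counts, an assumed 90% acceptability among those rated, and treating such a stop as not acceptable. The documents contain no contradiction on timing.

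**What to change.** 1. In the Schedule of Activities and Section 9.10, add the PAA at Day 1, completed with the witnessed first dose, and keep TW4 and TW8.
2. In Section 10.6.5.4, summarise Day 1, TW4 and TW8 with the number rated at each. Beside the ratings, report how many FAS participants discontinued treatment for taste or refusal. Add a sensitivity summary that counts them as not acceptable, and define that category in advance.
3. Add a taste/refusal category to the recorded reasons for discontinuation, so that step 2 can be carried out.
4. Optionally, use a form at the Early Discontinuation visit, reworded to refer to the last dose taken. The current form cannot be used there unchanged.

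The cost is a few minutes of site time at Day 1 and one extra discontinuation category. No new visit or blood sample is needed.
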